11.1.3.2 Unexpected adverse event

For the purposes of this study, an adverse event is considered unexpected when it varies in nature, intensity or frequency from information provided in the current adverse event list, the Investigator's Brochure, the package insert or when it is not included in the informed consent document as a potential risk.

11.1.4 Attribution

Attribution is the relationship between an adverse event or serious adverse event and the study treatment. Attribution will be assigned as follows:

- Definite – The AE is clearly related to the study treatment.
- Probable – The AE is likely related to the study treatment.
- Possible – The AE may be related to the study treatment.
- Unlikely - The AE is doubtfully related to the study treatment.
- Unrelated - The AE is clearly NOT related to the study treatment.

11.2 Procedures for AE and SAE Recording and Reporting

Participating investigators will assess the occurrence of AEs and SAEs at all participant evaluation time points during the study.

All AEs and SAEs whether reported by the participant, discovered during questioning, directly observed, or detected by physical examination, laboratory test or other means, will be recorded in the participant's medical record and on the appropriate study-specific case report forms.

The descriptions and grading scales found in the revised NCI Common Terminology Criteria for Adverse Events (CTCAE) version 4.0 will be utilized for AE reporting. All appropriate treatment areas should have access to a copy of the CTCAE version 4.0.

A copy of the CTCAE version 4.0 can be downloaded from the CTEP website at:

http://ctep.cancer.gov/protocolDevelopment/electronic_applications/ctc.htm.

CONFIDENTIAL

This document is confidential. Do not disclose or use except as authorized.

11.3 Reporting Requirements

The study must be conducted in compliance with FDA regulations, local safety reporting requirements, and reporting requirements of the principal investigator.

Each investigative site will be responsible to report SAEs that occur at that institution to their respective IRB. It is the responsibility of each participating investigator to report serious adverse events to the study sponsor and/or others as described below.

11.4 Reporting to the Study Sponsor

11.4.2 Serious Adverse Event Reporting

All serious adverse events that occur after the initial dose of study treatment, during treatment, or within 30 days of the last dose of treatment must be reported to the DF/HCC Overall Principal Investigator on the local institutional SAE form. This includes events meeting the criteria outlined in Section 11.1.2, as well as the following:

- Grade 2 (moderate) and Grade 3 (severe) Events – Only events that are unexpected and possibly, probably or definitely related/associated with the intervention.
- All Grade 4 (life-threatening or disabling) Events – Unless expected AND specifically listed in the protocol as not requiring reporting.
- All Grade 5 (fatal) Events – When the participant is enrolled and actively participating in the trial OR when the event occurs within 30 days of the last study intervention.

Note: If the participant is in long term follow up, report the death at the time of continuing review.

Participating investigators must report each serious adverse event to the DF/HCC Overall Principal Investigator within 24 hours of learning of the occurrence. In the event that the participating investigator does not become aware of the serious adverse event immediately (e.g., participant sought treatment elsewhere), the participating investigator is to report the event within 24 hours after learning of it and document the time of his or her first awareness of the adverse event. Report serious adverse events by telephone, email or facsimile to:

[name]

CONFIDENTIAL

This document is confidential. Do not disclose or use except as authorized.

[name] (phone)
[contact]
[name] (fax)

Within the following 24-48 hours, the participating investigator must provide follow-up information on the serious adverse event. Follow-up information should describe whether the event has resolved or continues, if and how the event was treated, and whether the participant will continue or discontinue study participation.

To ensure patient safety, every SAE, regardless of suspected causality, occurring in the following circumstances must be reported to Biothera within 24 hours of learning of its occurrence.

- After the patient has provided informed consent and until the patient has stopped study treatment/participation
- After protocol-specified procedures begin (e.g. placebo run-in, washout period, double-blind treatment) and until at least 28 days after the patient has stopped study treatment
- After the start of any period in which the study protocol interferes with the standard medical treatment given to a patient (e.g. treatment withdrawal during washout period, change in treatment to a fixed dose of concomitant medication) and until at least 28 days after the patient has stopped study treatment

Any SAEs experienced after this 28-day period should only be reported to Biothera if the investigator suspects a causal relationship to the study drug. Recurrent episodes, complications, or progression of the initial SAE must be reported as follow-up to the original episode within 24 hours of the investigator receiving the follow-up information.

An SAE occurring at a different time interval or otherwise considered completely unrelated to a previously reported one should be reported separately as a new event.

Information about all SAEs is collected and recorded on the Med Watch 3500A Form. The investigator must assess and record the relationship of each SAE to each specific study drug, complete the Med Watch Form in English, and fax the completed form within 24 hours to [name] at [contact].

All SAEs will have to be submitted to Apcer to be included in our safety database. SAEs need to be transmitted to APCER via email to [contact] or via fax to [contact]

CONFIDENTIAL

This document is confidential. Do not disclose or use except as authorized.

11.4.3 Non-Serious Adverse Event Reporting

Non-serious adverse events will be reported to the DF/HCC Overall Principal Investigator on the toxicity Case Report Forms.

11.5 Reporting to the Institutional Review Board (IRB)

Investigative sites within DF/HCC will report all serious adverse events directly to the DFCI Office for Human Research Studies (OHRS).

A copy of the submitted institutional SAE form should be forwarded to:

[name]
[name] (phone)
[contact]
[name] (fax)

11.6 Reporting to the Food and Drug Administration (FDA)

The DF/HCC Overall Principal Investigator, as holder of the IND, will be responsible for all communication with the FDA. The DF/HCC Overall Principal Investigator will report to the FDA, regardless of the site of occurrence, any adverse event that is serious, unexpected and reasonably related (i.e., possible, probable, definite) to the study treatment.

Unexpected fatal or life-threatening experiences associated with the use of the study treatment will be reported to FDA as soon as possible but in no event later than 7 calendar days after initial receipt of the information.

All other serious unexpected experiences associated with the use of the study treatment will be reported to FDA as soon as possible but in no event later than 15 calendar days after initial receipt of the information.

Events will be reported to the FDA by telephone ([name]) or by fax ([name]) using Form FDA 3500A (Mandatory Reporting Form for investigational agents). Forms are available at <http://www.fda.gov/medwatch/getforms.htm>.

11.7 Reporting to Hospital Risk Management

CONFIDENTIAL

This document is confidential. Do not disclose or use except as authorized.

Participating investigators will report to their local Risk Management office any subject safety reports or sentinel events that require reporting according to institutional policy.

11.8 Monitoring of Adverse Events and Period of Observation

All adverse events, both serious and non-serious, and deaths that are encountered from initiation of study intervention, throughout the study, and within 28 days of the last study intervention should be followed to their resolution, or until the participating investigator assesses them as stable, or the participating investigator determines the event to be irreversible, or the participant is lost to follow-up. The presence and resolution of AEs and SAEs (with dates) should be documented on the appropriate case report form and recorded in the participant's medical record to facilitate source data verification.

For some SAEs, the study sponsor or designee may follow-up by telephone, fax, and/or monitoring visit to obtain additional case details deemed necessary to appropriately evaluate the SAE report (e.g., hospital discharge summary, consultant report, or autopsy report).

Participants should be instructed to report any serious post-study event(s) that might reasonably be related to participation in this study. Participating investigators should notify the DF/HCC Overall Principal Investigator and their respective IRB of any unanticipated death or adverse event occurring after a participant has discontinued or terminated study participation that may reasonably be related to the study.

12. DATA AND SAFETY MONITORING

12.1 Data Reporting

12.1.1 Method

The QACT will collect, manage, and monitor data for this study.

12.1.2 Data Submission

The schedule for completion and submission of case report forms (paper or electronic) to the QACT is as follows:

CONFIDENTIAL

This document is confidential. Do not disclose or use except as authorized.

12. Form	13. Submission Timeline
Eligibility Checklist	Complete prior to registration with QACT
On Study Form	Within 14 days of registration
Baseline Assessment Form	Within 14 days of registration
Treatment Form	Within 10 days of the last day of the cycle
Adverse Event Report Form	Within 10 days of the last day of the cycle
Response Assessment Form	Within 10 days of the completion of the cycle required for response evaluation
Off Treatment/Off Study Form	Within 14 days of completing treatment or being taken off study for any reason
Follow up/Survival Form	Within 14 days of the protocol defined follow up visit date or call

12.2 Safety Meetings

The DF/HCC Data and Safety Monitoring Committee (DSMC) will review and monitor toxicity and accrual data from this trial. The committee is composed of clinical specialists with experience in oncology and who have no direct relationship with the study. Information that raises any questions about participant safety will be addressed with the Principal Investigator and study team.

The DSMC will meet quarterly and/or more often if required to review toxicity and accrual data. Information to be provided to the committee may include: up-to-date participant accrual; current dose level information; DLT information; all grade 2 or higher unexpected adverse events that have been reported; summary of all deaths occurring within 30 days for Phase 1 or 2 protocols; for gene transfer protocols, summary of all deaths while being treated and during active follow-up; any response information; audit results, and a summary provided by the study team. Other information (e.g. scans, laboratory values) will be provided upon request.

CONFIDENTIAL

This document is confidential. Do not disclose or use except as authorized.

12.3 Monitoring

Involvement in this study as a participating investigator implies acceptance of potential audits or inspections, including source data verification, by representatives designated by the DF/HCC Overall Principal Investigator (or Protocol Chair) or DF/HCC. The purpose of these audits or inspections is to examine study-related activities and documents to determine whether these activities were conducted and data were recorded, analyzed, and accurately reported in accordance with the protocol, institutional policy, Good Clinical Practice (GCP), and any applicable regulatory requirements.

All data will be monitored for timeliness of submission, completeness, and adherence to protocol requirements. Monitoring will begin at the time of participant registration and will continue during protocol performance and completion.

13. REGULATORY CONSIDERATIONS

13.1 Protocol Review and Amendments

This protocol, the proposed informed consent and all forms of participant information related to the study (e.g., advertisements used to recruit participants) and any other necessary documents must be submitted, reviewed and approved by a properly constituted IRB governing each study location.

Any changes made to the protocol must be submitted as amendments and must be approved by the IRB prior to implementation. Any changes in study conduct must be reported to the IRB. The DF/HCC Overall Principal Investigator (or Protocol Chair) will disseminate protocol amendment information to all participating investigators.

All decisions of the IRB concerning the conduct of the study must be made in writing.

13.2 Informed Consent

All participants must be provided a consent form describing this study and providing sufficient information for participants to make an informed decision about their participation in this study. The formal consent of a participant, using the IRB approved consent form, must be obtained before the participant is involved in any study-related procedure. The consent form must be signed and dated by the participant or the participant's legally authorized representative, and by the person obtaining

CONFIDENTIAL

This document is confidential. Do not disclose or use except as authorized.

the consent. The participant must be given a copy of the signed and dated consent document. The original signed copy of the consent document must be retained in the medical record or research file.

13.3 Ethics and Good Clinical Practice (GCP)

This study is to be conducted according to the following considerations, which represent good and sound research practice:

- US Code of Federal Regulations (CFR) governing clinical study conduct and ethical principles that have their origin in the Declaration of Helsinki
 - Title 21 Part 50 – Protection of Human Subjects
www.access.gpo.gov/nara/cfr/waisidx_02/21cfr50_02.html
 - Title 21 Part 54 – Financial Disclosure by Clinical Investigators
www.access.gpo.gov/nara/cfr/waisidx_02/21cfr54_02.html
 - Title 21 Part 56 – Institutional Review Boards
www.access.gpo.gov/nara/cfr/waisidx_02/21cfr56_02.html
 - Title 21 Part 312 – Investigational New Drug Application
www.access.gpo.gov/nara/cfr/waisidx_02/21cfr312_02.html
- State laws
- DF/HCC research policies and procedures
<http://www.dfhcc.harvard.edu/clinical-research-support/clinical-research-unit-cru/policies-and-procedures/>

It is understood that deviations from the protocol should be avoided, except when necessary to eliminate an immediate hazard to a research participant. In such case, the deviation must be reported to the IRB according to the local reporting policy.

13.4 Study Documentation

The investigator must prepare and maintain adequate and accurate case histories designed to record all observations and other data pertinent to the study for each research participant. This information enables the study to be fully documented and the study data to be subsequently verified.

Original source documents supporting entries in the case report forms include but are not limited to hospital records, clinical charts, laboratory and pharmacy records,

CONFIDENTIAL

This document is confidential. Do not disclose or use except as authorized.

recorded data from automated instruments, microfiches, photographic negatives, microfilm or magnetic media, and/or x-rays.

13.5 Records Retention

All study-related documents must be retained for the maximum period required by applicable federal regulations and guidelines or institutional policies.

14. STATISTICAL CONSIDERATIONS

14.1 Study Design/Endpoints

This is an open-label, single-arm, phase II clinical trial of Imprime PGG in combination with rituximab in patients with relapsed/refractory indolent B cell non-Hodgkin lymphomas. The primary endpoint is efficacy as measured by overall response rate. Secondary endpoints will include response duration, progression free survival at 1 year, , and rate of grade III and IV adverse events or discontinuation due to toxicity. We will estimate the proportion of patients alive without progression at 12 months after study entry. All patients must be followed for a minimum 12 months and must have scans at 6 and 12 months. No patients will be censored for this assessment. The one-year rate of being alive without progression will be estimated as a binomial proportion, and an exact binomial 90% confidence interval will be provided.

Patients will be accrued in a single stage design, with a goal accrual of 25 patients. Assuming a 30% response rate with rituximab alone, if the true but unknown rate of CR or PR is 50% with the addition of Imprime PGG, the probability of observing 11 or more patients with a response is 0.79. Therefore a study with 25 patients, in which an observed response rate of 11/25 (44%) would be considered worthy of further consideration.

We propose correlative studies quantifying Imprime PGG-bound and activated neutrophils, comparing both to the number and activation of unbound neutrophils from the same patient. We can examine the association between response to therapy (CR/PR vs. SD/Progression as best response).

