5.6 Criteria for Removal from Study Treatment

Participants will be removed from study when any of the criteria listed in Section 5.4 applies. The reason for study removal and the date the participant was removed must be documented in the study-specific case report form (CRF). Alternative care options will be discussed with the participant.

In the event of unusual or life-threatening complications, participating investigators must immediately notify the Principal Investigator, [name]. at [contact].

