14.2 Early Stopping- Toxicity

If 3 or more participants experience a grade 4 non-hematologic toxicity, the study will be suspended and the data will be reviewed by the data monitoring committee.

CONFIDENTIAL

This document is confidential. Do not disclose or use except as authorized.

Additionally, if at any point in the study any participant experiences a grade 5 toxicity, the study will be suspended and the toxicity data including attribution will be carefully reviewed. If these toxicity events are determined to be at least possibly related then the study will close.

[name] reserves the right to discontinue the study at any time.

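### The severe-toxicity endpoint names grades III and IV but not grade 5, so a fatal toxicity after the last dose can be left out of the rate

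*Combined protocol and SAP*

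**What the plan says.** **Endpoint.** Section 14.1 lists among the secondary endpoints the "rate of grade III and IV adverse events or discontinuation due to toxicity". It attaches no confidence level or decision rule to this rate. The exact 90% interval in that section belongs to the one-year proportion alive without progression.

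**Grade 5 elsewhere.** Section 14.2 has one rule for grade 4 non-hematologic toxicity and a separate one for grade 5: "if at any point in the study any participant experiences a grade 5 toxicity, the study will be suspended". The study closes if the event is judged at least possibly related. Section 11.4.2 also gives grade 5 events their own reporting entry: "When the participant is enrolled and actively participating in the trial OR when the event occurs within 30 days of the last study intervention".

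**Risk and timing.** Section 6.1 lists death among the rare but serious Imprime PGG toxicities. Section 6.2 describes viral infections up to a year after rituximab, some of them fatal. The study calendar in Section 9 puts the last dose on day 22, and Section 5.5 follows patients for one year after treatment.

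**Late deaths.** A Note in 11.4.2 adds: "If the participant is in long term follow up, report the death at the time of continuing review". Section 11.8 asks investigators to tell the Overall Principal Investigator and the IRB of unanticipated deaths or events after participation has ended that may reasonably be related. It gives no time limit.

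**The concern.** Read literally, the endpoint counts a grade 3 event and can miss a fatal one. A reader who takes the reported rate as the trial's summary of severe toxicity would not expect its worst outcome to be outside the definition.

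The secondary issue is that the grade 5 rule in 14.2 can act only once the death is known. If the follow-up year counts as long-term follow-up, the Note lets even a treatment-related death wait for continuing review, which sits badly with a rule that applies at any point in the study.

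**Working it through.** **1. Is grade 5 covered by implication?** Toxicity is graded by CTCAE version 4.0 (Sections 6 and 11.2). Sections 11.4.2 and 14.2 both treat grade 5 as separate from grade 4. Naming only III and IV in 14.1 therefore does not include grade 5 on its face.

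**2. Does the discontinuation arm cover it?** It may cover a death during the four weekly doses. It cannot cover a death after the last dose (nominally day 22, later if doses are delayed), because no treatment remains to be discontinued. Such a death is counted only if the patient also had a grade III or IV event or an earlier discontinuation for toxicity.

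**3. Size.** The plan gives no figure for this rate, so there is none to reproduce. Assumptions: a denominator of 25 (the planned sample size), and exact (Clopper-Pearson) 90% limits, a level borrowed from the one-year endpoint. Each uncounted death is worth 1/25 = 4.0 percentage points.

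With x events in n = 25, the lower limit is the 5th percentile of Beta(x, n − x + 1), or 0 when x = 0. The upper limit is the 95th percentile of Beta(x + 1, n − x).

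| Other patients with a qualifying event | Rate as defined (90% CI) | Rate with the death counted (90% CI) |
|---|---|---|
| 0 (extreme case) | 0/25 = 0% (0 to 11.3%) | 1/25 = 4% (0.2 to 17.6%) |
| 6 (assumed) | 6/25 = 24% (11.0 to 42.0%) | 7/25 = 28% (13.9 to 46.2%) |

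**4. Does any design figure move?** Section 14.1 states a probability of 0.79 of at least 11 responses in 25 if the true rate is 50%. The exact binomial tail P(X ≥ 11 | 25, 0.50) is 0.788, which reproduces it. The toxicity definition does not enter that calculation.

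**5. Late deaths, text against text.** The 30-day window ends at about day 22 + 30 = 52. About 365 − 30 = 335 of the 365 follow-up days (92%) lie beyond it. What applies then depends on how that year is classed:

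- *Active participation.* Section 5.5 and Section 14.1 require the year of follow-up, 14.1 with scans at 6 and 12 months. The study calendar schedules toxicity assessment at both visits. On this reading the grade 5 entry in 11.4.2 applies, with its 24-hour report to the Overall Principal Investigator.
- *Long-term follow-up.* Footnote 6 of the calendar calls the 10-week visit the end-of-study visit. On this reading the Note applies.

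The first reading has more support. The second is not excluded, because neither category is defined.

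**6. Other routes.** None of these settles the question for every related late death:

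- Late events go to the drug supplier on suspicion of a link to the study drug: "Any SAEs experienced after this 28-day period should only be reported to Biothera if the investigator suspects a causal relationship to the study drug".
- The FDA limit, "in no event later than 7 calendar days after initial receipt of the information", covers unexpected fatal or life-threatening events and runs from receipt.
- Section 5.6 says "In the event of unusual or life-threatening complications, participating investigators must immediately notify the Principal Investigator", but in a section on removal from study treatment.

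**The case against.** A fair defence has four parts.

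- **Nothing is hidden.** The safety objective in 1.3 is broader than this one rate. Adverse events are collected to the final visit, death is a serious adverse event, and a grade 5 toxicity suspends the study. A toxic death would also be a failure in the one-year proportion alive without progression. This stands: the omission is from one summary rate. A reader might infer that fatal toxicities would go unrecorded, and the documents do not support that.
- **The case is narrow.** It needs a death after the last dose in a patient with no other qualifying event, and the 0/25 base is the extreme. Section 2.1.3 reports serious adverse events in 25% to 90% of cancer patients, depending on the study (apart from two single-IND studies). Serious events are not the same as grade III and IV events, but a base of zero is unlikely. This also stands, and is why the 6/25 row is shown.
- **Late related deaths have a route.** Section 11.8 sends them to the Overall Principal Investigator, and the calendar favours the reading with a 24-hour report. A reader might infer that no prompt report is required at all. The text supports only an ambiguity.
- **Institutional rules may fill the gap.** Sections 11.3 and 13.3 bind sites to local reporting requirements and institutional policies that are not reproduced. This stands as a limit on what can be concluded.

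**Conclusion.** The endpoint point holds. As worded, 14.1 leaves out a fatal toxicity after the last dose in a patient with no other qualifying event. The size is 4 percentage points per such death, assuming a denominator of 25. No frequency is given, and the primary endpoint, sample size and power are unaffected.

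The reporting point is minor. The Note in 11.4.2 makes no exception for related deaths and can be read against 14.2. The calendar and the mandatory follow-up favour the 24-hour reading, but the end-of-study label leaves the matter open.

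Two stronger readings are tempting and are not supported:

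- A reader might infer that the monitoring committee lacks a deadline it needs for the grade 5 rule. Section 14.2 names that committee only in the grade 4 rule. The grade 5 sentence does not make suspension wait for it, and the information list in 12.2 is permissive.
- A reader might infer that a delayed report would let a calculable number of further patients enrol. The continuing-review interval and the institutional reporting rules are not given, so the delay cannot be estimated.

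**What to change.** 1. In 14.1, define the endpoint as the rate of grade 3 or higher (grades 3 to 5) adverse events or discontinuation due to toxicity.
2. Reconcile 11.4.2 and 11.8 with 14.2. State whether the follow-up year is active participation or long-term follow-up, limit the continuing-review Note to deaths not considered related, and make 11.8 consistent with that choice. The rule in 14.2 is not changed.

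The cost is wording in three sections, with no new visits or tests. The downside is a slightly higher reported toxicity rate if such a death occurs, and possibly a few more expedited reports.
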